Study site	Koulikoro and Banamba districts in Koulikoro Region, Mali
Primary Objective	The primary objective of this study is to estimate the impact of a self-monitoring tool (ChARM), used as a teaching/monitoring device, on the CHWs respiratory rate counting accuracy when assessing children under the age of 5 years with suspected pneumonia symptoms.
Study Intervention	Basic training on ChARM device and application of the device on children under five with suspected pneumonia symptoms.
Primary Outcome	Acute Respiratory Illness (ARI) Case fatality rate
Secondary Outcomes	Respiratory rate counting accuracy Proportion of pneumonia cases detected and treated by CHWs Proportion of suspected severe pneumonia cases referred by CHWs to the CSCom Proportion of suspected pneumonia cases in the community who sought care from a CHW Accuracy in drug management and procurement requests
# of CHWs	Intervention Group A: approximately 49 (1/3 of the CHWs, randomly selected) Intervention Group B: approximately 49 (1/3 of the CHWs, randomly selected) Control Group C: approximately 50 (1/3 of the CHWs, randomly selected)
Main Inclusion Criteria	 Be currently providing iCCM services on a full-time basis to the populations they are serving. Have completed the Malian Ministry of Health basic community health care worker training provided as part of the 2016-2020 Strengthening Maternal, Newborn and Child Health project.

	 Are using a device (a respiratory timer) as part of their basic MoH training package, or have a cell phone to use to count the respiratory rates of children under five with suspected symptoms of pneumonia. Be willing to participate in a trial to study the impact of using ChARM as a selfmonitoring tool to improve the capacity to detect pneumonia.
Main Exclusion Criteria	 CHWs in conflict ridden geographical areas within the district or not, providing consistent services on a full-time basis to the populations they are serving. CHWs not willing to participate in the trial. CHWs who do not have a device (watch, respiratory timer or cell phone) to support measurement of respiratory rates and who are not routinely counting respiratory rate to diagnose suspected pneumonia. CHWs who did not complete the MoH basic training for CHWs provided through the 2016-2020 Strengthening Maternal, Newborn and Child Health program.

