- Intervention Group A: CHWs trained in ChARM and using ChARM as a self-monitoring tool for 8 months while counting respiratory rate of children under 5 visually using a timer.
- Intervention Group B: CHWs trained in ChARM and using ChARM as a self-monitoring tool for 4 months while counting respiratory rate of children under 5 visually using a time; then discontinue using ChARM and continue to monitor the respiratory rate visually using a timer only for the remaining 4 months.
- Control Group C: CHWs who did not receive the ChARM training and will be monitoring the respiratory rate of children under 5 visually using a timer only, as per the MoH traditional training.

Throughout the study 3 independent Field Monitors will follow each group's participants in both Banamba and Koulikoro (i.e. one Field Monitor will follow 1/2 CHWs in Group A in Banamba and 1/2 CHWs in Group A Koulikoro; the Field Monitors responsible for Groups B and C will also follow one study group each, in both areas). The Field Monitors will be responsible for both testing the accuracy of the CHWs' ability to count respiratory rate and for collecting data during the study from the CHW reports and drug records. The Field Monitors will receive the same training as the CHWs in the Intervention Groups A and B, and additional training on data collection and observation protocol. The Field Monitor will test the CHWs' capacity to count respiratory rate during three intervals:

[figure not shown]
- Before the ChARM training
- 4 months after initiating the use of the ChARM device
- 8 months after initiating the use of the ChARM device (which corresponds to 4 months after the ChARM device will be discontinued for group B).

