At each of the three measures, the Field Monitor will test CHWs on their visual respiratory rate counting capacity using a timer against the ChARM automated readings and review supporting data sources. To maintain the study observation periods comparable, and save on the additional logistics costs, the intervention will be rolled out in Koulikoro 1 month after it has been rolled out in Banamba. Therefore, for the 2nd and 3rd direct observation the Field Monitors will begin first in Banamba and then one month later in Koulikoro. This will allow time for the Field Monitors to carry out the site visits required for each district for each of the measurements (approximately 24 visits per Field Monitor per district). As a result, the 2nd and 3rd measure for Groups A and B and C in Banamba will be at 4 months and 8 months, and the same groups in Koulikoro will be measured one month later, but still at 4 and 8 months.

The qualitative evaluation will be undertaken only in the Intervention Groups A and B using In-depth Interviews (IDIs) with CHWs, Field Monitors and the Technical Director of the Health centre responsible for the CHWs. In total 25 IDIs will be carried out. The Study Coordinator will be responsible for supporting the research and qualitative researcher who will be carrying out the IDIs. In total, anticipated number of IDIs are:

- Field Monitors 3 IDIs, one interview with each one
- Technical Director of Health Centre (Directeur Technique du Centre/CSCom) (DTCs) 10 IDIs (5 in Banamba and 5 in Koulikoro)
- Community Health Workers 12 IDIs

Figure I: RCT Flow Chart

4. Randomization

An epidemiologist not directly involved in the research project will perform randomization of clusters. Due to the nature of the intervention, blinding is not possible, however to ensure reduced measurement bias, data on the effect of the intervention will be collected by independent data collectors; not involved in the intervention delivery. The unit of randomization will be the community health worker.

5. Study Setting

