CHWs randomized to intervention Groups A and B will be trained to use the ChARM device and in data collection requirements (filling out the self-monitoring sheet and getting consent from caregivers of children under 5). For the 4 months of Phase 1, CHWs in Intervention Groups A and B will count the respiratory rate of all children under five presenting with symptoms of cough or cold, using the timer and visual counting simultaneously with the ChARM device. Group C will count the respiratory rate using visual counting with the timer only.

Phase II: (4 months)

The second phase of the study will take place from July-November 2018. In the first month of this phase Field Monitor will retest CHWs for the 2nd time in all groups on their breath counting capacity against the ChARM automated reading and record results. The Field Monitor will also review the CHW monthly reports, consultation/referral forms, the drug supply forms, as well as the self-monitoring forms filled in by the CHWs. (Please see Annex 1 for a copy of all forms).

During Phase II, Group A will continue to count the respiratory rate of all children under five presenting with symptoms of cough and/or cold, simultaneously using the timer and visual counting and the ChARM device. However, once Group B is tested, the CHWs in that group will stop using ChARM and will start to count respiratory rate using only the visual counting measured by the timer. Group C will continue to count respiratory rate using only visual counting measured by the timer.

An interim analysis of the data from Phase II will be undertaken by an independent researcher (to be chosen by the DSMB) once testing has been completed in the three groups.

Phase III: (4 months)

This phase has three main activities. The first is the 3rd testing by Field Monitors of CHWs in all groups of their breath counting capacity against the ChARM automated reading and the recording of results. The Field Monitors will also review the CHW monthly reports, consultation/referral forms, the drug supply forms, as well as the self-monitoring forms filled in by the CHWs.

Once retested, CHWs in Group A will stop using ChARM and will start to count respiratory rate only using the visual counting measured by the timer. CHWs in Groups B and C will continue to count respiratory rate; only using visual counting measured by the timer.

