- 3. CHWs who do not have a device (a respiratory timer) to measure respiratory rate and who are not routinely counting respiratory rate to diagnose suspected pneumonia.
- 4. CHWs who did not complete the MoH basic training for CHWs provided through the 2016-2020 Strengthening Maternal, Newborn and Child Health program.

Enrollment

- 1. Approval from the Ministry of Health Mali and the Regional Directorate of Health, Koulikoro will be obtained to enroll CHWs providing iCCM services in the districts of Koulikoro and Banamba in the study.
- 2. Subsequently the local study coordinator will visit the MoH district level staff and share the letters of approval from the MoH and regional directorate with the facilities responsible for the CHWs working in the Banamba and Koulikoro districts to formalize the enrollment.
- 3. All consenting women and men seeking care from the CHW for a child under 5 presenting with symptoms of pneumonia (i.e. cough and/or cold) will be invited to provide consent and enroll in the study.

8. Intervention Groups

The intervention is a training in ChARM device offered to CHWs providing iCCM services to children under-five in the districts of Banamba and Koulikoro.

Once all CHWs in the two districts have been randomized into the three groups and had their breath counting skill tested using ChARM as a global measure, the CHWs randomized to Groups A and B will receive a 1-day training on the ChARM device. During the training, CHWs in intervention groups will learn how to use the ChARM device as a self-monitoring tool by comparing the respiratory rate they count visually when using the timer against ChARM's automated read-out during assessment of all children under-5 years presenting with symptoms of pneumonia (cough and/or cold). CHWs will be instructed to record the two measurements on the self-monitoring sheet and to continue to record the child's respiratory rates, treatment and referrals on the MoH forms they routinely fill out.

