All CHWs in Groups A and B will use the both ChARM and visual breath counting using the timer for the first 4 months of the study. In the case of a discrepancy where there is enough variation that the CHW visual counts using a timer and the ChARM reading would put the child in different categories (i.e. rapid or non-rapid respiration) then the CHW will be instructed to use the ChARM reading for filling the section on the MoH form for Individual Case Management of a Sick Child (Fiche Individuelle de Prise en Charge de l'Enfant Malade – PEC) form. (Annex 1).

In the fifth month the Field Monitor will retest CHWs in Groups A and B, using the ChARM device as a global measure. The Field Monitor will also review the CHW monthly reports, PEC consultation/referral forms, drug supply forms, and the self-monitoring forms filled in by the CHWs.

For months 5 – 8, CHWs randomized to Group A will continue to use ChARM as a self-monitoring tool, continue to count respiratory rate visually using a timer and to compare and record the two measurements. Group B CHWs will discontinue using ChARM and only count respiratory rate visually using a timer. Both groups will continue to record the child's respiratory rates, treatment and referrals on the MoH forms they routinely fill out.

9. Control Group

All CHWS in the three groups received training on the basic CHW curriculum given by the Ministry of Health as off August 2017. In the training, they all received respiratory timers and were trained to count respiratory rate using those timers through classroom instruction, videos, and hands on practice in a health facility setting.

The control group (Group C) composed of 1/3 of the CHWs in Banamba and 1/3 of the CHWs in Koulikoro will have completed the basic MoH training, but will not receive the additional ChARM training or receive the device. Throughout the study Group C will count respiratory rate visually using a timer only and record the child's respiratory rates, treatment and referrals on the MoH forms they routinely fill out when assessing and treating a child presenting with symptoms of pneumonia. The Field Monitor for Group C in both districts will measure their breath counting competency, using the ChARM device as a global measure following the same testing intervals as the intervention groups A and B.

10. Study Trainers

The Intervention trainer for demonstrating how to count respiratory rates will be selected according to the following criteria:

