16.1. Field Monitors

The Field Monitors (described above) will be responsible to collect data at three different time periods, before the intervention, 4 months after the intervention begins and 8 months after the intervention begins. There will be one Field Monitor each for Groups A, B and C who will cover those groups in both districts. They will be practicing health

professionals and have participated in the 1-day ChARM training in which they will receive in-depth understanding of the required data collection forms and the ChARM device. Field Monitors will conduct 3 site visits to test the CHWs respiratory rate counting ability using a timer against the ChARM automated reading and record both readings. They will review and document the number of cases assessed for pneumonia, treated and/or referred by CHWs during the three testing periods.

Data Collection

i) Quantitative Data Collection:

Written informed consent will be taken from participating Community Health Workers in the Intervention and Control Groups, and from parents and caregivers of all children under five who will have their respiratory rates counted using the ChARM device. It will be made clear that eligible participants are under no obligation to participate in this study. In addition, the time burden associated with being involved in this study will be clearly outlined during the consent process.

Data from the CHW self-monitoring sheets filled out by Intervention Groups A and B will be reviewed and documented by the Field Monitor. The Field Monitor will also measure all CHWs respiratory rate counting capacity using ChARM as a global standard and collect routine CHW data three times during the study. This routine data is found in both the CHW monthly reports and the consultation/referral forms. Data from drug supply forms filled out by CHWs will also be collected to identify any variations that may occur due to more accurate pneumonia diagnosis by CHWs as a result of using ChARM and to triangulate this data with the consultation forms and other sections of the monthly report.

ii) Oualitative Data Collection:

Qualitative data collection will only take place in the intervention Groups A and B. Written, informed consent will be taken from CHWs, Field Monitors and MoH Technical Director of Health Centre (Directeur Technique du Centre/CSCom) participating in in-depth interviews. (Consent Forms - Annex 3, Questions for In-depth interviews - Annex 4).

Outcomes:

Primary outcome:

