Acute Respiratory Illness (ARI) Case fatality rate

Secondary outcomes:

Respiratory rate assessment accuracy

Proportion of pneumonia cases detected and treated by CHWs

Proportion of suspected severe pneumonia cases referred by CHWs to the CSCom

Proportion of suspected cases of pneumonia in the community who sought care from a CHW

Accuracy in drug management and procurement requests

Sample size:

48 clusters with average size of 50 suspected ARI cases per cluster per arm (over 8 months) are sufficient to detect a 30% reduction in the ARI case-fatality rate (from 20% at baseline), with 80% power and 5% significance. Differences in all secondary outcomes are powered above 80% within this sample size.

iCCM Curriculum Training: Intervention & Control sites

Participants: CHWs in Koulikoro and Banamba districts (n=148)

Time frame: Completed as part of CRC program implementation in Mali (December 2016 – August 2017)

Responsibility: CRC/MoH Mali Trainers

Training Material: Ministry of Health iCCM curriculum for CHWs -18-day curriculum including classroom instruction and hands on training.

Intervention Training: Intervention sites

Participants: CHWs in Koulikoro (n≅49) and Banamba (n≅49) districts.

Time Frame: After iCCM curriculum training; 9 months-1month for training CHWs in ChARM and 8 months for monitoring.

Responsibility: External Trainers and Study coordinator

- A. CHWs trained in ChARM and the self-monitoring data collection format.
- B. Submission of regular MoH monthly reports, consultation referral forms, drug supply forms.
- C. In-depth interviews for CHWs, Field Monitor and the Technical Director of Health Centres (Directeur Technique du Centre/CSCom) on their perception of ChARM tool and recommendations for future use as a teaching tool and/or scale up by the MoH.

Control Sites

CHWs in Koulikoro and Banamba districts (n=49)

Time frame: 8 months-including initial measurement of respiratory rate counts using a timer against ChARM's automated reading and subsequently repeating the measurement twice during the study.

- A. Pneumonia diagnosis as per usual practice of visually counting respiratory rate using a respiratory timer.
- B. Submission of regular monthly reports, consultation/referral reports and drug supply reports for review by Field Monitors.

12. Data Processing and analysis

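### With one Field Monitor per study group, monitor drift after baseline in the counting test cannot be separated from the ChARM effect in comparisons with Group C, or in A versus B after month 4

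*Protocol*

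**What the plan says.** The protocol gives the monitor assignment in three places, and they agree.

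- Section 16.1, Field Monitors: "There will be one Field Monitor each for Groups A, B and C who will cover those groups in both districts".
- Trial Methodology and Sample Size: "the Field Monitors responsible for Groups B and C will also follow one study group each, in both areas".
- Control Group: "The Field Monitor for Group C in both districts will measure their breath counting competency, using the ChARM device as a global measure".

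The workload is given as "approximately 24 visits per Field Monitor per district". At baseline, 4 and 8 months the monitor tests each CHW's timed visual count against the automated ChARM reading and records both. The same monitor abstracts routine data from the CHW's forms.

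Groups A and B are treated alike up to the second test. After that, "once Group B is tested, the CHWs in that group will stop using ChARM", while Group A continues to month 8.

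The primary objective concerns "respiratory rate counting accuracy". The Outcomes list places "Respiratory rate assessment accuracy" among the secondary outcomes, with ARI case fatality as primary. The Randomization section says that blinding is not possible and relies on data collectors who do not deliver the intervention.

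**The concern.** When one assessor sees all of one group and nobody else, a difference between groups may come from the intervention or from the assessor. Here the assessor runs the test that answers the primary objective. If one monitor gradually changes how the test is set up, timed, repeated or recorded, the mean of one whole group moves and the other groups do not. A difference of A or B from C at 4 or 8 months would then have a rival explanation. Because this follows from who visits whom, neither more CHWs nor a different model restores the missing information on the counting test.

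**Working it through.** **1. Does the workload fit one monitor per group?** Figure II gives 75 CHWs in Banamba and 73 in Koulikoro. One third is 75/3 = 25.0 and 73/3 = 24.3, which agrees with the stated figure of about 24 visits per monitor per district. The example in Trial Methodology and Sample Size, which speaks of half of Group A in each district, is loosely worded. Taken with the workload and the other statements, it means the part of Group A that lives in that district.

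**2. Which contrasts can be estimated?** Take 3 groups by 3 test times. Use 3 group terms, 2 time terms and 3 treatment terms: ChARM at month 4 (common to A and B), A at month 8 and B at month 8. That makes 8 columns. The four contrasts are ChARM versus C at month 4, and A versus C, B versus C and A versus B at month 8.

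| Design and model | Columns | Rank | The four contrasts |
|---|---|---|---|
| As written, no monitor effect | 8 | 8 | all estimable |
| As written, constant monitor effect | 10 | 8 | all estimable, because of the baseline test |
| As written, monitor effect varying over time | 14 | 9 | none estimable |
| Monitors crossed with groups, varying over time | 14 | 14 | all estimable |

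In the design as written, the drift of the B monitor relative to the A monitor can be estimated at month 4, because both groups have had the same treatment by then. Their relative drift at month 8 cannot be estimated from the tests. Nor can the drift of the C monitor relative to the A monitor at month 4.

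**3. How sensitive is the A versus B check at month 4?** Assume 49 CHWs per group, outcome SD 1, a change-score test and baseline-to-follow-up correlation r. The protocol does not give r.

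SE = sqrt(2(1 − r) × 2/49), and the drift detectable with 80% power is (1.96 + 0.84) × SE = 2.80 × SE.

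- r = 0: SE 0.286, detectable drift 0.80 SD
- r = 0.5: SE 0.202, detectable drift 0.57 SD
- r = 0.7: SE 0.157, detectable drift 0.44 SD

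**4. What would drift do to A versus C with no true effect?** For a relative drift d between the two monitors, the probability of rejection at nominal 5%, two-sided, is 1 − Φ(1.96 − d/SE) + Φ(−1.96 − d/SE).

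| Assumed d (SD) | r = 0 | r = 0.5 |
|---|---|---|
| 0.05 | 5.4% | 5.7% |
| 0.1 | 6.4% | 7.9% |
| 0.2 | 11% | 17% |
| 0.4 | 29% | 51% |

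For example, at r = 0.5 and d = 0.2, d/SE = 0.2/0.202 = 0.99, so 1 − Φ(0.97) + Φ(−2.95) = 0.168. A drift of 0.2 SD between the A and B monitors would go undetected by the month-4 check with probability 1 − 0.168 = 0.83.

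**The case against.** The protocol has real safeguards. The CHW makes the count, a device gives the reference, and both readings are recorded. Monitors share the same ChARM training and receive further training on an observation protocol. They are described as independent of intervention delivery, although Field Supervision and Quality Control blurs this by mentioning them in connection with CHW training. Entries are checked for range and consistency, the study coordinator supervises, and the DSMB reviews data quality and departures from the operating procedures. Those procedures are not shown and may contain more. All this limits monitor influence, and it makes large drift harder to presume. It does not break the aliasing.

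Three stronger readings are tempting, and the documents do not support them.

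- *That A versus B at month 4 is the only internal check.* CHWs in A and B also record their own count and the ChARM reading on self-monitoring sheets, Group A to month 8 and Group B to month 4. Comparing these with the monitor's test gives a partial check within each group. It is imperfect: the children differ and the same monitor documents the sheets. It does not cover Group C.
- *That no later work could undo the problem for any monitor-collected data.* Data abstracted from monthly reports, consultation and referral forms and drug supply forms share the aliasing, but those records could in principle be abstracted again. Only the live counting test is irreversible.
- *That serious inflation of error has been shown.* Every drift size above is an assumption. At 0.05 to 0.1 SD the effect is small, and the protocol does not define the accuracy measure that would give the SD a scale.

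**Conclusion.** The aliasing is certain from the text and needs no assumption. For the counting test, drift after baseline is inseparable from the ChARM effect in every comparison with Group C, and in A versus B after month 4. A constant additive offset is not a problem, provided the analysis uses the baseline test.

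The practical size is unknown. Under the assumptions above it runs from negligible (about 5.4% to 5.7% rejection at 0.05 SD) to serious (29% to 51% at 0.4 SD). A reader might infer that the listed primary outcome, ARI case fatality, is undermined. What is shown here concerns the counting test, and no claim about case fatality is made. The point should still be fixed, because the counting test answers the stated primary objective, the Group C monitor has no check, and the remedy is cheap before data collection and unavailable for this test afterwards.

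**What to change.** In Trial Methodology and Sample Size, Control Group and section 16.1, replace one monitor per group with the same three monitors crossed with groups. Suggested text:

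*In each district, the CHWs of each group are allocated at random, in numbers as equal as possible, to the three Field Monitors. Each CHW keeps the same monitor at baseline, 4 and 8 months. All monitors use the same written test and abstraction procedure in every group. The baseline-adjusted analysis accounts for monitor.*

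This gives 75/9 = 8.3 CHWs per group per monitor in Banamba and 73/9 = 8.1 in Koulikoro. Details of the model can sit in the SAP. The allocation can be fixed before the first visit, because groups are assigned before the baseline test: "Once all CHWs in the two districts have been randomized into the three groups and had their breath counting skill tested", and only then are A and B trained.

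**Cost.** No extra staff or visits are needed: each monitor still makes about 25 visits in Banamba and 24 in Koulikoro, already covers both districts and already has the same training. Routes must be re-planned and 2 degrees of freedom are spent. Each monitor would now see all three groups, which brings some risk of contrast bias or contamination of Group C. The common procedure, and a rule that self-monitoring sheets from A and B are not taken to Group C CHWs, guard against this.

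**Limit.** Crossing removes additive monitor effects only. Expectation bias remains, because monitors know which group they are testing.
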